#### **Demographics**

Descriptive statistics will be applied for the demographic data of all subjects. Pre to post-operative comparisons will be made for all outcome measures at the specific data collection time points. Summary statistics for continuous variables may include subject count, mean, standard deviation, minimum and maximum values.

#### **ADVERSE EVENTS**

Unanticipated Adverse Device Effect (UADE), Serious Adverse Events (SAE's) & ADVERSE EVENTS (AE's)

#### Overview

Procedural and device related events will be described and collected on the AE form. It is the responsibility of the operating surgeon/s to be aware and note the adverse effects from the package insert/instructions for use by the manufacturer/sponsor. (See appendix A) The number of subjects experiencing each adverse event percentage or proportion of the total number of subjects experiencing each adverse event will also be reported. All adverse events shall be reported in an interim and/or final report of the clinical investigation. All device deficiencies related to the identity, quality, durability, reliability, safety or performance of the investigational medical device shall be documented throughout the clinical investigation and appropriately managed by the sponsor.

Potential intraoperative and early postoperative complications, related to all total ankle replacements may include:

- pain;
- sudden drop in blood pressure intra-operatively due to the use of bone cement;
- damage to blood vessels;

- temporary or permanent nerve damage resulting in pain or numbness of the affected limb;
- cardiovascular disorders including venous thrombosis, pulmonary embolism, or myocardial infarction.
- hematoma;
- delayed wound healing; and
- deep wound infection (early or late) which may necessitate removal of the prosthesis.
- rarely an arthrodesis of the involved joint or amputation of the limb may be required.

Potential, late postoperative complications can include:

- pain;
- bone fracture by trauma or excessive loading, particularly in the presence of poor bone stock;
- peri-articular calcification or ossification, with or without impediment to joint mobility; and
- inadequate range of motion due to improper selection or positioning of components or peri-articular calcification.

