## *Adverse Event Data Collection and Reporting* The following definitions from 21 CFR.

## Adverse Event (AE)

Adverse event means any untoward medical occurrence associated with the use of an intervention in humans,

whether or not considered intervention-related

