### **Recording and Reporting Adverse Events – Investigator & Sponsor Responsibilities**

#### Recording and Reporting Adverse Events - Investigator Responsibilities

The Investigator will:

- Record protocol required AE's together with an assessment as recorded in the Adverse Event Case Report Forms;
- Supply Wright Medical, upon their request, with any additional information related to the safety reporting of a particular AE

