#### Recording and Reporting Adverse Events - Wright Medical Responsibilities

Wright Medical is responsible for the classification of AEs and ongoing safety evaluation of the study and will:

• review the Investigator's assessment of all AEs; determine and document, in writing, the seriousness of the adverse event and relationship of the adverse event to the implanted components.

In case of disagreement between Wright Medical and the Investigator, Wright Medical shall:

- communicate both opinions to concerned parties; and
- as required, ensure that the IRB/EC/REC and regulatory authorities are informed or significant new information involving the product during the study.

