### Table 2. Study schedule.

Procedures	Pre-op	Op.	6 mo +/-30 days	1 yr +/-60 days	2 yr +/-60 days	5 yr +/-60 days	7 yr +/-60 days	10 yr +/-60 days	Study Close
Informed Consent	Х								
Inclusion/Exclusion Criteria	Х								
Medical History & Demographics	Х								
Operative Surgical procedure/device		Х							
PROMIS Global Health	Х		Х	X	Х	Х	Х	Х	
Ankle Osteoarthritis Score (AOS)	Х		Х	Х	Х	Х	Х	X	
FAOS Questionnaire	Х		Х	Х	Х	Х	Х	Х	
Total Ankle Replacement			Х	Х	Х	Х	Х	Х	
Radiographic Assessment	Х		Х	Х	Х	Х	Х	Х	
Adverse Event Assessment		Х	Х	Х	Х	Х	Х	Х	
End of Study		 							Х
Surgical Intervention 									
*Sponsor-approved Unscheduled Visit 									

 $1\&^2$  These are not scheduled time point events but will be observed for throughout study participation.

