#### 1. Adverse Evets

Adverse Event (AE) is defined as any untoward medical occurrence, unintended disease or injury, or untoward clinical signs (including abnormal laboratory findings) in subjects, users, or other persons, whether or not related to the investigational medical device. All adverse events shall be reported in an interim and/or final report of the clinical investigation. Frequency of these complications will be summarized by according to Preferred Term (PT) and System Organ Class (SOC) using Medical Dictionary for Regulatory Affairs (MedDRA 18.0).

The Investigator will follow up subjects who experience an AE until it is either resolved, determined to be chronic, stable, or, until the subject's participation in the study ends. Prior to completion of the study, the Investigator will complete the Adverse Event Status Update Case Report Form to document any AE's previously reported as ongoing.

Intra-operative and post-operative complications, whether device-related or not, suspected or not complications will be reported as adverse events. Potential intraoperative and early postoperative complications, related to all total ankle replacements may include:

- a. pain;
- b. sudden drop in blood pressure intra-operatively due to the use of bone cement;
- c. damage to blood vessels;
- d. temporary or permanent nerve damage resulting in pain or numbness of the affected limb;

e. cardiovascular disorders including venous thrombosis, pulmonary embolism, or myocardial infarction.

f. hematoma;

- g. delayed wound healing; and
- h. deep wound infection (early or late) which may necessitate removal of the prosthesis.
- i. rarely an arthrodesis of the involved joint or amputation of the limb may be required.

Potential, late postoperative complications can include:

a. pain;

b. bone fracture by trauma or excessive loading, particularly in the presence of poor bone stock;c. peri-articular calcification or ossification, with or without impediment to joint mobility; andd. inadequate range of motion due to improper selection or positioning of components or periarticular calcification.

Additionally, these complications will be further categorized and reported as device related, or procedure related and outcome.

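### The protocol leaves open whether non-serious events judged unrelated go on the AE form, while SAP Tables 4.1 to 4.3 are titled as all-event tables

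*Protocol*

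**What the plan says.** **What goes on the form.** The protocol's Adverse Events, Overview section states: "Procedural and device related events will be described and collected on the AE form". Under Investigator Responsibilities, the duty is: "Record protocol required AE's together with an assessment as recorded in the Adverse Event Case Report Forms". No section says which events the protocol requires.

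**What counts, is reviewed and is reported.** Later in the same Overview: "All adverse events shall be reported in an interim and/or final report of the clinical investigation". The protocol's definition takes in any untoward occurrence, "whether or not considered intervention-related". Under Wright Medical Responsibilities, the sponsor reviews the investigator's "assessment of all AEs; determine and document, in writing, the seriousness of the adverse event", and must "determine and document, in writing, the seriousness of the adverse event and relationship of the adverse event to the implanted components". The SAP's adverse-event section also defines events irrespective of relatedness and adds: "Intra-operative and post-operative complications, whether device-related or not, suspected or not complications will be reported as adverse events". Only after that does it sort them into device related and procedure related.

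**Serious events.** The protocol sends these to the sponsor within 24 hours, related or not, on a separate SAE form.

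**Tables.** In the SAP's Listing of Tables, the titles of 4.1, 4.2 and 4.3 have no relatedness limit. Tables 4.4.1 and 4.4.2 are restricted to procedure-related and device-related events. Table 4.5.1 covers serious events and Table 4.5.2 related serious events.

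**Schedule.** The row "Adverse Event Assessment" is ticked at the operative visit in SAP Table 2. In the protocol's Schedule of Events it is first ticked at 6 months.

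**The concern.** Implant safety is a stated secondary objective in the protocol and a safety objective in the SAP. Whether an event is related should be decided after it has been recorded, and the protocol gives the sponsor a part in that decision. If relatedness also decides whether a non-serious event is written down at all, the site's first judgement becomes final for the events it leaves out. The provision for sponsor and investigator to disagree then has nothing to act on for those events.

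The reporting risk is twofold. Tables titled as all adverse events might contain a narrower set. And the SAP's Safety Analysis section plans summaries by instrumentation type and COFAS type, which are comparable only if every site recorded to the same scope.

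**Working it through.** No arithmetic in the plan bears on this point, and no adverse-event rate or count is given to reproduce. The check is a comparison of the text.

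**Step 1. Scope, place by place**

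| Place | Scope of events |
|---|---|
| Protocol, Overview, first sentence | Procedural and device related |
| Protocol, Investigator Responsibilities | Those the protocol requires (undefined) |
| Protocol, Overview, later sentence on reports | All |
| Protocol, AE definition | All, related or not |
| Protocol, sponsor review | All |
| Protocol, SAE reporting | All serious, related or not |
| SAP, adverse-event section | All, related or not |
| SAP, Tables 4.1 to 4.3 | All, by title |

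The first row speaks directly to the form. The second implies a subset, and the first row is the only place that offers one for non-serious events. Nothing says which statement governs.

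**Step 2. Which events depend on the reading**

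| Event | Broad reading | Narrow reading |
|---|---|---|
| Serious, any cause (S) | Recorded | Recorded |
| Non-serious, related to device or procedure (R) | Recorded | Recorded |
| Non-serious, judged unrelated to both (U) | Recorded | May be left off |

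Only U is exposed. The protection for S extends to events that are serious under the protocol's definition. That definition does not list intervention to prevent permanent impairment, which the SAP's does.

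**Step 3. Effect on the tables**

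Assume that events from the SAE form feed the adverse-event tables. Table 4.2 then holds S + R + U under the broad reading and S + R under the narrow one. In the narrow case its non-serious part is R, which is what Tables 4.4.1 and 4.4.2 already show between them, while its serious part, like Table 4.5.1, is still of any cause. One table would carry two scopes. The shortfall is U/(S + R + U), and the documents give none of S, R or U.

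**Step 4. Effect on subgroup summaries**

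If every site used the narrow reading, subgroups would be compared on a common, understated scope. A distortion caused by differences in reading needs two conditions: sites read the instruction differently, and sites differ in their mix of instrumentation or COFAS types. The documents neither show nor exclude either condition.

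**Step 5. Schedule**

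The protocol's Operative Procedure Information section sends intraoperative complications to the AE form. The SAP's operative tick therefore agrees with that section, and the protocol's own schedule is the outlier.

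**The case against.** The strongest reply is that the narrow reading is only an inference. A reader might infer that the protocol collects *only* related events, but its sentence has no exclusive wording, and the same section, the definition and the sponsor's review duty all point to every event. The AE case report forms are listed in the protocol's appendix but not reproduced in the public document, and they may settle the scope. This stands: the narrow reading is possible, not established.

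A reader might also infer that events judged unrelated never reach the sponsor. That is wrong for serious events, and for non-serious ones it is true only if a site reads narrowly.

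Nor do the documents support the inference that early loosening would go unseen. Pain is listed among both early and late complications, and inadequate range of motion among the late ones. AOS and FAOS are scored, and radiographs read for loosening and subsidence, at every follow-up visit. Surgery related to the replacement has its own form. What could be lost is the adverse-event record and its relationship review, not all trace of the problem.

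A reader might want a multiple. If 30% to 60% of non-serious events were judged unrelated, ignoring serious events gives a broad-to-narrow ratio of 1/0.7 = 1.4 to 1/0.4 = 2.5. Serious events are kept under both readings. With share unrelated u and serious share s, the ratio of all events is therefore 1/[s + (1 − s)(1 − u)]. For s = 20% it is 1/0.76 = 1.3 to 1/0.52 = 1.9. Both u and s are assumed, and the comparison sets a wholly narrow site against a wholly broad one. None of these figures is evidence about this study.

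On the schedule, a first tick at 6 months does not bar recording events since surgery, and the serious-event and device-failure rules apply throughout. That mismatch is minor.

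**Conclusion.** The conflict over the AE form's scope is real and can be seen from the text alone. It goes beyond missing detail, because a site could follow the Overview and the investigator instruction faithfully and still omit events that the SAP's tables claim to count. The exposure is confined to non-serious events the site judges unrelated to both device and procedure, and it arises only under the narrow reading. If that reading was used anywhere, Tables 4.1 to 4.3 would present any-cause serious events plus related-only non-serious events as all adverse events. The size of the effect cannot be estimated from the documents.

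This rests on two assumptions: that the unreproduced case report form instructions do not already settle the scope, and that serious-event reports feed the adverse-event tables. The primary survivorship endpoint is not affected. The point should be corrected before the next safety report, mainly so that related-only counts are not published as all-cause rates.

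**What to change.** 1. In the protocol, state one collection scope that agrees with the definition: all adverse events from surgery onward are recorded whether or not considered related, and relatedness is classified afterwards. Define the events investigators must record in the same terms. A scope limited to the operated limb plus serious events would not resolve the conflict. It is narrower than both definitions and would drop non-serious procedural events elsewhere, such as the cement-related fall in blood pressure that the protocol itself lists.
2. Tick the adverse-event row at the operative visit in the protocol's schedule, to match SAP Table 2.
3. For data already collected, establish from the case report form instructions and from each site which scope was applied, and footnote Tables 4.1 to 4.3 accordingly. Do not relabel them as related-only without that check, since the label could be false.

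**Cost.** The protocol requires IRB approval of amendments, so this is more than a memo. Sites will complete more AE forms, and the reported rate may rise somewhat. The SAP's Study Design section records that enrollment closed at 155 patients, so a wording change acts only on remaining follow-up. If a site had been recording narrowly, its data will have a before-and-after break in scope that must be footnoted. The footnotes themselves need no new patient data.

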## *Adverse Event Data Collection and Reporting* The following definitions from 21 CFR.

## Adverse Event (AE)

Adverse event means any untoward medical occurrence associated with the use of an intervention in humans,

whether or not considered intervention-related

#### Serious Adverse Event (SAE)

An adverse event (AE) or suspected adverse reaction is considered "serious" if, in the view of either the investigator or sponsor, it results in any of the following outcomes:

- death, or
- a life-threatening adverse event, or
- inpatient hospitalization or prolongation of existing hospitalization, or
- a persistent or significant incapacity or substantial disruption of the ability to conduct normal life functions

## Adverse Event Status Updates (AE)

The Investigator will follow up subjects who experience an AE until it is either resolved, determined to be chronic,

stable, or, until the subject's participation in the study ends.

Prior to completion of the study, the Investigator will complete the Adverse Event Status Update Case Report Form to document any AE's previously reported as ongoing.

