**ISO 14155:2011** also specifies general requirements intended to protect the rights, safety and well-being of human subjects, ensure the scientific conduct of the clinical investigation and the credibility of the results, define the responsibilities of the sponsor and principal investigator, and assist sponsors, investigators, ethics committees, regulatory authorities and other bodies involved in the conformity assessment of medical devices.

Osteolysis - pathological destruction or disappearance of bone tissue.

Subsidence- sinking or settling in bone, as of a prosthetic component of a total joint implant.

Study Title	The INFINITY ™ Total Ankle Replacement Follow-up (ITAR)					
Study Design	Prospective, multi-site, multi-year post-market clinical follow-up study					
Study Group	Primary/Unilateral and/or bilateral Total Ankle Arthroplasty subjects implanted with INFINITY TM Total Ankle System					
N Subjects	200 with 10 sites					
Follow-Up Schedule	Subject enrollment will consist of a Pre-operative, Operative, 6 months, 1 yr., 2 yr., 5yr., 7 yr., 10 yr., and an unscheduled visit as needed.					
Primary Objective	Evaluate the long-term survivorship of the INFINITY ™ implant over 10 years					
Secondary Objective(s)	
 
Secondary objectives assessed will be to:
 
Identify and assess the implant for component loosening and/or subsidence, any osteolysis and/or cyst formation through radiographic evaluation early and throughout the lifetime of the implant.
 
Compare the improvements in self-reported physical, mental, and social health measures from pre-op through 10 years post operatively; assessed by PROMIS® Global Health.
 
Compare pain and functional improvement in the Ankle Osteoarthritis Score (AOS), which is a visual analogue scale specifically designed as a modification of the Foot Function Index.
 
Compare the improvement in patient/physician reported function scores from pre-op through 10 years post-operatively, assessed by the FAOS questionnaire.
 
Compare satisfaction of total ankle replacement post operatively utilizing a four point scale
 
Identify and report the safety of the implant in terms of complications and adverse events.
 
					

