## **Device** Failure

Subjects will be considered a treatment failure, and will be withdrawn from the study if any sections of the device (tibial or talar metal components) have been removed at any time during their participation. This should be reported onto the adverse event form. In addition, any surgical intervention during study participation that relates to their total ankle replacement will be reported on the surgical intervention case report form.

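### Removing a metal component withdraws the subject and so ends active safety follow-up, leaving what happens after device failure largely unrecorded

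*Protocol*

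**What the plan says.** **Withdrawal.** Protocol, Device Failure: the section classes certain subjects as having failed treatment. Its rule is that such a subject "will be withdrawn from the study if any sections of the device (tibial or talar metal components) have been removed at any time". The same section says of this failure, "This should be reported onto the adverse event form". It also sends surgery related to the replacement to the surgical intervention form, but only for surgery that happens while the subject is participating.

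**End of adverse-event follow-up.** Protocol, Adverse Event Status Updates: follow-up runs until the event is resolved, chronic or "stable, or, until the subject's participation in the study ends". The SAP's adverse-event section has the same stopping rule: "determined to be chronic, stable, or, until the subject's participation in the study ends".

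**Complications foreseen.** The Protocol's adverse-event Overview lists deep infection that can lead to the prosthesis being taken out. The next item is "rarely an arthrodesis of the involved joint or amputation of the limb may be required".

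**Reporting promised.** The SAP makes long-term safety an objective (Safety objectives). It also says that "these complications will be further categorized and reported as device related, or procedure related and outcome", plans a separate serious-event table that includes death and permanent impairment, and plans to tabulate deaths and their causes over the 10-year follow-up (Patient Disposition and Accounting).

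**Study group.** Protocol synopsis: "Primary/Unilateral and/or bilateral Total Ankle Arthroplasty subjects implanted with" the study device.

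**The concern.** Each rule is unremarkable alone. Together, they stop observation at the point where a serious device problem may still be unfolding. A subject whose infected implant is removed leaves the study that day, with the infection possibly unresolved and further surgery possibly still to come.

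The loss is informative, because the device's worst outcome triggers it. It is also imposed by the plan. The right to leave voluntarily is covered separately under Subject Withdrawal or Discontinuation, whereas the Device Failure rule removes subjects who may be willing to stay. The SAP's Missing Data section excludes patients with missing data and imputes nothing, so the analysis cannot repair the gap.

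At stake are the safety outputs: the outcome column for events that led to removal, the serious-event table, and the count of deaths. A reader of the 10-year report could take these as complete for all implanted subjects when, for failed devices, they stop at failure.

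**Working it through.** The plan states no figure on this point, so the check is mainly a reading of the sections against each other.

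1. **Trigger.** Removal of a tibial or talar metal component leads to withdrawal of the subject (Protocol, Device Failure). Exchange of the polyethylene insert alone is not named as a trigger.
2. **Consequence for adverse events.** Withdrawal ends participation, and the end of participation ends follow-up even if the event is unresolved (Protocol, Adverse Event Status Updates; SAP, adverse events). Neither text makes an exception for the event that caused the removal.
3. **Consequence for surgery.** The surgical intervention form covers surgery during participation only, so a later operation on that ankle falls outside it.
4. **Is there follow-up elsewhere?**
   - SAP, Safety Analysis and Reporting, includes all implanted subjects. That fixes who is analysed, not how long they are observed.
   - SAP, Report Timing of survivorship assessment, keeps revised patients in the analysis. It adds no data collection after revision.
   - The Protocol's section on investigator reporting of serious events requires significant new information within 24 hours and gives no end date. It applies only once the investigator learns of something.
   - The Protocol's investigator responsibilities for adverse events include supplying further information when the sponsor asks.
   - The Adverse Event Status Update form records events previously reported as ongoing, before study completion. It does not provide for contact with a withdrawn subject.
   - The remote route by post or telephone (Protocol, Study Duration) covers patient-reported outcome forms only.
5. **What is captured and what is not.**
   - Captured: the removal; an arthrodesis or amputation at the same operation (Device Failure; SAP, Subsequent secondary surgical interventions); and the failed ankle's survivorship event.
   - Not actively sought: the final outcome of an event ongoing at removal, a later or staged arthrodesis or amputation, a further serious event, and death.
6. **Bilateral subjects.** The synopsis admits them, and both withdrawal and identification are by subject. Other text suggests one index ankle: the exclusion criterion speaks of the ankle being considered, the operative form of an index joint, and the medical history form lists a contralateral ankle replacement among other joints. The documents do not settle whether one subject can have two study ankles.
7. **Size, by assumption.** The SAP gives 155 subjects, and neither document gives a removal rate. Number affected = 155 × assumed 10-year removal proportion:
   - at 5%: 155 × 0.05 = 7.75, about 8 subjects;
   - at 15%: 155 × 0.15 = 23.25, about 23 subjects.

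**The case against.** The strongest reply is that this is a deliberate and coherent choice. The SAP frames its safety objective around the implant, and once the implant is out there is nothing left to follow. Removal is the endpoint, it is recorded on two forms, and the subject stays in the survivorship and safety sets. Serious-event updates have no stated end date, and the sponsor can request more.

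Much of this stands. A reader might infer that arthrodesis and amputation go unrecorded altogether. They do not: either one, done at the removal operation, is reported and tabulated. A reader might also infer that the primary endpoint is damaged for the failed ankle. It is not, because the failure is counted. Nor is safety reported only for implants that stayed in place, since events up to and including removal are recorded.

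Two further readings go too far. One is that a bilateral subject's second study implant is certainly lost. That follows only if both ankles are study ankles, which the documents leave open. The other is a total of subject-years lost. That would need an assumed time of removal and would treat every affected subject as otherwise completing 10 years, although the Protocol itself raises loss to follow-up.

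The reply does not close the gap. Passive and on-request reporting is not follow-up of a subject who has no scheduled contact. The SAP also promises event outcomes and deaths over the full period without limiting them to subjects whose implant is in place.

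**Conclusion.** The concern holds in a limited form. As written, the plan requires no active follow-up after a metal component is removed. Later events and unresolved outcomes in those subjects are recorded only if they happen to reach the investigator or the sponsor asks. This selectively truncates the long-term safety, event-outcome, serious-event and death summaries; survivorship of the failed ankle is unaffected. If both ankles of a bilateral subject are study ankles, the rule also ends observation of the intact implant and costs primary-endpoint information on that side.

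That the gap exists follows from the text and needs no assumed rate. Its extent is uncertain: about 8 to 23 of 155 subjects if 5% to 15% have a removal by 10 years, with the rate an assumption and the number of bilateral subjects unstated. The change should be made. The SAP still describes the 10-year analysis as to come, and outcomes not collected now may not be recoverable later.

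**What to change.** The changes concern data collection only and alter no treatment.

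- **Protocol, Device Failure:** count the ankle as failed on the date of removal. Keep a willing subject in the study for adverse and serious adverse events, further surgery on that ankle (including arthrodesis and amputation) and vital status at the scheduled time points. The right to withdraw is unchanged.
- **Protocol, Study Duration:** extend the post and telephone route to these data. It now covers patient-reported outcome forms only.
- **Protocol, Adverse Event Status Updates, and the matching SAP text:** follow an event that led to removal until it is resolved, chronic or stable, whether or not the component has been removed.
- **Bilateral subjects:** state whether both ankles can be study ankles and, if so, that an unrevised contralateral study ankle continues the schedule.
- **SAP:** add a listing of final outcomes after removal.

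The cost is a protocol amendment, brief contacts for a few subjects, and some re-consent. Enrolment is closed, so any subjects already withdrawn under the current rule would have to be re-contacted and asked. The reported serious-event count may rise slightly.
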